EQ-5D-Y	EuroQol group 5-dimension quality of life questionnaire for youth
ILAR	International League of Associations for Rheumatology
IMP	Investigational Medical Product
JIA	Juvenile Idiopathic Arthritis
MISS	Methotrexate Intolerance Severity Score
n	number
NSAID	Nonsteroidal Anti-Inflammatory Drugs
OPT-JIA	Ondansetron Premedication Trial in Juvenile Idiopathic Arthritis
PGA	Physician Global Assessment
RCT	Randomized Controlled Trial
SAE	Serious Adverse Event
SAP	Statistical Analysis Plan
SUSAR	Suspected Unexpected Serious Adverse Reaction

4 Introduction

4.1 Preface

Methotrexate is the most widely used disease-modifying anti-rheumatic drug (DMARD) for the treatment of children with Juvenile Idiopathic Arthritis (JIA). In children, methotrexate side effects such as nausea, vomiting and abdominal discomfort can lead to conditioned methotrexate intolerance with anticipatory nausea/vomiting and avoidance behaviours (in up to 50% of children). Methotrexate intolerance leads to poor adherence to optimal dosing or to stopping the medication altogether. Children who cannot adhere to optimal dosing or stop methotrexate may require expensive biologic medications to control their JIA.

The Ondansetron Premedication Trial in Juvenile Idiopathic Arthritis (OPT-JIA) is a registry-based pragmatic adaptive superiority randomized clinical trial to evaluate if routine premedication with the anti-emetic ondansetron reduces methotrexate intolerance and increases the proportion of children with JIA able to continue taking methotrexate, resulting in a better quality of life and more cost-effective medication use. OPT-JIA is a Health Canada regulated trial that adheres to the International Council for Harmonization of Technical Requirements for Pharmaceuticals for Human Use (ICH) guidelines for design, analysis and reporting.

All OPT-JIA data is collected via the Canadian Alliance of Pediatric Rheumatology Investigators (CAPRI) JIA Registry. The CAPRI Registry captures information on clinical characteristics, outcomes and adverse events of children with JIA across all Canadian pediatric rheumatology centres, at every visit to clinic. The Registry started in 2017, and as of October 2023, it contains information on >1200 children. OPT-JIA does not have fixed time intervals for data collection. Data is collected for one year after study enrolment at clinic visits that are scheduled according to patient needs.

4.2 Scope of the analyses

The OPT-JIA protocol contemplates three main analyses: safety analyses every 6 months, one interim efficacy analysis and a final analysis of safety and efficacy. The 6-monthly safety analysis is descriptive and consists of a Table summarizing the characteristics of enrolled subjects and a Table listing reported adverse events.

This Statistical Analysis Plan describes the details of the interim (preliminary) efficacy analysis and the final analysis of safety and efficacy. It specifies the changes made relative to the analysis plan outlined in the OPT-JIA protocol V3, approved by Health Canada in September 2020.

5 Study Objectives and Endpoints

5.1 Study Objectives

(ICH E3; 8.)

The aim of OPT-JIA is to determine the effectiveness of prophylactic use of ondansetron in patients with JIA starting methotrexate in Canadian pediatric rheumatology practices (intervention), compared to as-needed use in those children who develop nausea/vomiting (control).

Specific Objectives:

To compare:

- 1) The proportions of patients remaining on methotrexate with no intolerance between the two groups one year after starting methotrexate (primary endpoint).
- 2) The safety and tolerability of premedication with ondansetron, compared to as needed use.
- 3) The 1-year cumulative incidence of: a) methotrexate intolerance, b) attainment of inactive disease, c) biologic medication initiation
- 4) The mean quality of life scores and methotrexate intolerance severity scores between the two groups 4-8 months after starting methotrexate.

OPT-JIA also collects information on impacts on quality of life (to calculate health utilities) and medication utilization that will enable a future cost-effectiveness analysis.

5.2 Endpoints

(ICH E9; 2.2.2)

Primary endpoint:

Proportion of subjects that remain on methotrexate with no intolerance one year after starting methotrexate. Intolerance is defined as ≥ 6 points in the English or French versions of the validated Methotrexate Intolerance Severity Score, MISS [1, 2]. The MISS questionnaire can be found in the appendix.

Secondary endpoints:

- 1) frequency and cumulative incidence of adverse events and any serious unexpected suspected adverse drug reactions (SUSARs).
- 2) the cumulative incidence of methotrexate intolerance within one year;
- 3) the cumulative incidence of attainment of inactive disease within one year defined by Wallace criteria [3] as modified by Guzman et al [4];
- 4) the cumulative incidence of starting a biologic medication within one year; and
- 5) the mean quality of life scores in the Quality of My Life scale 4-8 months after starting methotrexate [5];
- 6) the mean scores in the MISS questionnaire 4-8 months after starting methotrexate.

To enable future cost-effectiveness analysis, the EuroQol Collaboration 5-dimension scale for quality of life for youth parent-proxy questionnaire (EQ-5D-Y) is completed at every visit, for calculation of quality-adjusted life years [6], and medication costs will be calculated using the prices from the Ontario Drug Benefit Formulary [7].

Assessment of outcomes are completed at all clinic visits scheduled as per medical need using the CAPRI Registry (usual practice is every 1-4 months). OPT-JIA does not include additional trial-specific visits.

6 Study Methods

6.1 General Study Design and Plan

(ICH E3;9) (ICH E3; 9.2, 9.7.1, 11.4.2.7. ICH E9; 3.3.2)

Children (ages 4-16 years) in the CAPRI JIA Registry who are starting methotrexate for the first time are eligible to participate in OPT-JIA. The target sample is 176 children followed for one year after starting methotrexate. Patients are followed every 1-4 months as clinically indicated. Outcomes are assessed via online data collection into the Registry at all clinic visits. The OPT-JIA protocol calls for an interim efficacy analysis completed after 90 children are recruited. The analysis results are to be used by an independent data and safety committee (DSC) to review for any needed adjustments to the target sample size, or study termination for success or futility.

OPT-JIA is a CAPRI JIA Registry-based pragmatic adaptive superiority RCT. OPT-JIA trial schema is reproduced in Figure 1 below.

Registry-based: The trial uses infrastructure already in place for the CAPRI JIA Registry [8].

Pragmatic: Broad inclusion criteria and simple outcome assessments compatible with usual care.

Adaptive: OPT-JIA is a Planned Sample-Size Re-Estimation Adaptive Trial as described by Bhatt & Metha [9].

Superiority: Designed to test superiority (as opposed to non-inferiority) of ondansetron premedication.

RCT: Treatments assigned by block randomization and analyses adjusted for post-randomization imbalances. Patients are randomized online via the REDCap [10] Registry plug-in using a 1:1 block randomization by Canadian region of residence and patient weight (<15Kg, 15-30Kg, >30Kg) with randomly assigned block size to ensure allocation concealment [11]. There is no blinding.

[figure not shown]

Figure 1: Trial schema for the Ondansetron Premedication Trial in Juvenile Idiopathic Arthritis (OPT-JIA).

Children in the intervention group are prescribed premedication with oral ondansetron (2 mg if <15Kg, 4 mg if 15-30Kg, 8 mg if >30Kg) to be taken one hour before each weekly methotrexate dose, followed by two additional doses every 6-8 hours if awake. All children receive methotrexate and folic/folinic acid as per the rheumatologist's usual practice. Current North American guidelines recommend a dose of methotrexate of 10-20 mg/m² weekly subcutaneously or orally to a maximum of 25mg/week, at the discretion of physician and family [12, 13]. Folic/folinic acid is commonly used as 1mg orally daily or 5-10mg orally weekly.

Children in the control group receive methotrexate and folic/folinic acid as per the physician's usual practice. Those who report nausea/vomiting during regular care are prescribed ondansetron at the same dose and schedule as above, as per the attending rheumatologist's discretion. This is the current practice at BC Children's Hospital and other Canadian centres.

Ondansetron is offered in three forms: tablets (4mg, 8mg), oral solution (4mg/5ml) and oral disintegrating tablets (4mg, 8mg). Tablets can be swallowed or crushed and mixed with food. Ondansetron will be prescribed as tablets, unless the physician and family decide to use liquid or oral disintegrating tablets instead. The dose will be the same.

6.2 Inclusion-Exclusion Criteria and General Study Population

(ICH E3;9.3. ICH E9;2.2.1)

Subject inclusion criteria:

1. Ages 4-16 years
2. Diagnosis of JIA as per International League of Associations for Rheumatology ILAR criteria [14]
3. Followed at a CAPRI centre in Canada
4. Starting methotrexate to control JIA manifestations (arthritis, uveitis, psoriasis). (Female subjects of child bearing potential who are taking methotrexate for JIA cannot be pregnant, breastfeeding, or planning a pregnancy while on the drug and females of childbearing potential who are sexually active must use highly effective medically acceptable contraception. Subjects who stop methotrexate during the study will also discontinue ondansetron.)
5. Informed written consent to participate
6. Participating in the CAPRI JIA Registry

Subject exclusion criteria:

1. Previous use of methotrexate
2. Known hypersensitivity to ondansetron or any components of its formulations
3. Known hypersensitivity to other 5-HT3 antagonists
4. Known congenital Long-QT syndrome
5. Patients taking other medicinal products that lead to either QT prolongation or electrolyte abnormalities
6. Because the serotonin syndrome may occur when ondansetron is combined with other agents that may affect the serotonergic neurotransmitter system, patients receiving any of the serotonergic and/or neuroleptic drugs listed below will be excluded:
 - Triptans, SSRIs, SNRIs, lithium, sibutramine, fentanyl and its analogues, dextromethorphan, tramadol, tapendadol, meperidine, methadone, pentazocine or St. John's Wort (*Hypericum perforatum*), MAOIs, linezolid, methylene blue.
7. Patients who are pregnant or breastfeeding, or are sexually active and unwilling to practice an acceptable method of birth control.
8. Family unable to complete questionnaires in English or French

6.3 Randomization and Blinding

(ICH E3; 9.4.3, 9.4.6. ICH E9; 2.3.1, 2.3.2)

Patients are assigned 1:1 online after confirming eligibility, using the Registry and block randomization by Canadian region and patient weight to one of two groups:

Intervention	routine premedication with oral ondansetron (2 mg if <15Kg, 4 mg if 15-30Kg, 8 mg if >30Kg; 3 doses a week)
Control	oral ondansetron at the same dosing, prescribed only to those who develop methotrexate-induced nausea/vomiting during usual care.

There is no blinding (masking) of treatment assignment.

6.4 Study Assessments

(ICH E3; 9.5.1. ICH E9; 2.2.2)

Visit	Baseline	Every Visit	Visit Month 12
History and examination	x	x	x
QOL questionnaire	x	x (\pm 14)	x (\pm 14)
MISS	x	x (\pm 14)	x (\pm 14)
Actionable AEs	x	x	x
SAEs	x	x	x
SUSARs	x	x	x
Concomitant medication	x	x	x
Methotrexate use and dose	x	x	x
Ondansetron use and dose	x	x	x

Analysis Time Windows

Visit (target day)	Lower bound (days)	Upper bound (days)
Baseline (0)	N/A	N/A
Every visit to clinic (time window not applicable)	N/A	N/A
Month 4-8 (180)	120	240
Month 12 (364)	308	420

7 Sample Size

(ICH E3; 9.7.2. ICH E9; 3.5)

Our primary outcome statistic is the ratio of two proportions (relative risk, RR): the proportion of randomized children remaining on methotrexate with no intolerance in the intervention group divided by the same in the control group. Our sample size calculation is based on expressing the RR in the log scale and using established formulas for standard errors [15, 16]. With $p<0.05$, power of 90% and expected methotrexate continuation with no intolerance of 50% in the control group and 75% in the intervention group the result is 79 evaluable subjects per group. We will aim to recruit 176 subjects total to allow for up to a 10% dropout rate.

8 General Analysis Considerations

8.1 Timing of Analyses

The “6-monthly” safety analysis is completed before the meetings of the DSC and its precise timing depends on the dates booked for DSC meetings.

The interim analysis was planned at the time 90 subjects had been recruited in OPT-JIA but it was rescheduled with approval of the DSC and the Steering Committee, to occur on September 30th, 2023 due to slow recruitment, as explained in section 8.5 below.

The final analysis is to be conducted after the final sample size is achieved or at the time the study is stopped. All subjects enrolled in the study at that time will complete a one-year follow-up and will be included in the final analysis.

8.2 Analysis Populations

(ICH E3; 9.7.1, 11.4.2.5. ICH E9; 5.2)

The primary analysis will be conducted on the intention-to-treat population, including all randomized subjects. A secondary per-protocol analysis will be conducted on those subjects who received the assigned intervention for at least 3 months (ondansetron and methotrexate in the intervention group, methotrexate in the control group). Because it was clear at the time of interim analysis that some patients stopped methotrexate before 3 months due to intolerance, the per protocol analysis was modified to also include patients who stopped the medication before 3 months due to intolerance or toxicity.

8.3 Covariates and Subgroups

(ICH E3; 9.7.1, 11.4.2.1. ICH E9; 5.7)

The following covariates at baseline will be used to define if post-randomization imbalances have occurred: age, sex, months since JIA diagnosis, JIA category, active joint count, physician global assessment of disease activity, parent global assessment of wellbeing, c-reactive protein level, erythrocyte sedimentation rate, body weight strata, previous treatment and presence of uveitis.

If imbalances have occurred ($p<0.1$), the imbalanced variables will be used in logistic regression models to adjust efficacy estimates. OPT-JIA does not include any subgroup analyses.

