8.5.9 Documentation of Interim Analyses

All interim analysis data files, preliminary statistical output and final interim analysis report for the DSC will be preserved in the OPT-JIA Trial folders at the institutional computer servers controlled by the BC Children's Hospital in Vancouver, under the custody of [name]. Copies of all email communications pertaining the interim analysis between the study biostatisticians, study PI and the chair of the DSC will also be preserved in these folders.

9 Summary of Study Data

All variables will be summarized separately for subjects assigned to the intervention and to the control group and shown in side-by-side columns in tables in that order. Descriptive categorical variables at baseline will be summarized as frequencies and percentages. Descriptive continuous variables at baseline will be summarized as medians and 25th and 75th centiles. Efficacy categorical variables will be summarized as frequency and percentages. Efficacy continuous variables (MISS scores and quality of life scores) will be summarized as means and standard deviations.

Between-groups comparisons of baseline characteristics will be made using Fisher exact tests for categorical variables and the Wilcoxon rank sum test for continuous variables, and the corresponding p value reported. All tests will be double sided and p values <0.05 will be considered statistically significant.

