9.5 Treatment Compliance

Compliance with ondansetron and methotrexate is queried at each medical visit by the attending physician (local investigator) and reported in the physician case report forms. Parents are asked to confirm in writing in the parents' questionnaire how many ondansetron tablets were given to their child with the previous dose of methotrexate.

Since this is a pragmatic trial to test effectiveness in usual medical practice, there will be no pill counts or measurement of blood medication levels as part of this trial.

10 Efficacy Analyses

The final efficacy analysis will be conducted after the last recruited trial participant has had an opportunity to be followed for 60 weeks from the date of recruitment (52 weeks plus an 8-week window of observation and data entry). The final dataset will then be verified and locked.

As per the OPT-JIA protocol (V3, 2-Sept-2020), the final analysis will be an intention to treat analysis including all randomized participants irrespective of whether they completed the trial, received or not the trial interventions, or dropped out. A secondary modified per-protocol analysis will be conducted on those subjects who received the assigned intervention for at least 3 months or stopped medications before 3 months for intolerance or toxicity.

All statistical analysis will test the null hypothesis of no differences between intervention and control groups. The a priori alternative hypothesis is that the intervention group will have better outcomes than the control group.

Logistic regression models will be used to adjust effect estimates for post-randomization imbalances in the two groups (intervention, control). Baseline variables with a p value <0.1 in the baseline comparison of intervention and control groups will be considered post-randomization imbalances and adjusted for, if any.

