Our primary outcome statistic is the ratio of two proportions (relative risk, RR): the proportion of randomized children remaining on methotrexate with no intolerance one year after enrolment in the intervention group divided by the same in the control group. Subjects stopping ondansetron or methotrexate for toxicity or lack of efficacy will be counted as trial failures in calculations for the primary endpoint, irrespective of their MISS scores. A 95% CI for the RR will be calculated and the null hypothesis will be rejected if the confidence interval is entirely above 1. Considering that an interim analysis will be conducted, the alpha used in the final analysis will be 0.05 minus the alpha used in the interim analysis. As stated above, due to patient withdrawals and the fact that OPT-JIA did not have fixed-date visits, a number of patients was expected not to have a documented primary endpoint within the 52-week window, and a decision was made to use instead the Kaplan Meier estimates of the probability of success for calculations of the relative risk.

Cumulative incidence of methotrexate intolerance within one year: The Kaplan Meier survival analysis estimate of the cumulative incidence of a MISS score of 6 or more points within 52 weeks of study enrollment, as defined above. Kaplan-Meier curves will be constructed separately for intervention and control groups and the curves will be compared using the log-rank test.

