With the agreement of the Steering Committee and the Data and Safety Committee, the interim analysis took place at an earlier stage than initially specified because of the slow enrolment into the study. The interim analysis was planned by [name] with the assistance of [name] and discussed with the PI, [name], in March 2023. It was discussed and approved at the steering committee call of April 21, and at the Data and Safety Committee call on May 8, 2023, and further confirmed with the DSC chair via email on October 5, 2023. The approved plan was to extract information from the REDCap database on September 30, and this was postponed to October 6, to allow time for responses to remaining queries to be verified by site principal investigators. The sample sizes for the interim analysis were smaller than had been expected, and hence there were only 27 patients on whom success or failure had been definitively determined at the time the interim analysis was conducted with data extracted on October 6th, 2023. There were an additional 17 participants who were still on the trial, with at least one follow-up visit but not yet to their 52-week visit. We therefore used the Kaplan-Meier (KM) statistical analysis technique separately in each group to estimate the probability of success in each group in a way that would make some use of the partial information provided by the patients with incomplete follow-up periods.

We used the KM method to estimate the probability of success at 52 weeks and formed the relative risk (RR) by dividing the estimated probability for the intervention group by the estimated probability for the control group. The statistical properties of the RR are better expressed on the log scale, so we computed the log of this ratio, which is equivalent to the difference between the two logged survival probabilities. We computed the standard error for this difference using the separate standard errors for each logged survival probability and computed the confidence interval on this log scale using the standard normal (Wald) method. The same KM methods will be applied for the final efficacy analysis.

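### The covariate adjustment (logistic regression on baseline variables with p<0.1) does not match the Kaplan-Meier relative risk that is now primary, and leaves out region, a randomisation factor

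*SAP*

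**What the plan says.** **Adjustment rule.** Section 6.1 describes the design as having "analyses adjusted for post-randomization imbalances". Section 8.3 lists 12 baseline variables and says that, if any is imbalanced at p<0.1, "the imbalanced variables will be used in logistic regression models to adjust efficacy estimates". Section 10 restates this for the final analysis: "Baseline variables with a p value <0.1 in the baseline comparison of intervention and control groups will be considered post-randomization imbalances". Section 9 sets the screening tests: "Fisher exact tests for categorical variables and the Wilcoxon rank sum test for continuous variables".

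**Primary statistic.** Section 10.1 first describes a ratio of two proportions. It then says that, because some children will have no documented endpoint, "a decision was made to use instead the Kaplan Meier estimates of the probability of success for calculations of the relative risk". Section 15 gives the construction: "dividing the estimated probability for the intervention group by the estimated probability for the control group", with a Wald interval on the log scale built from the two separate standard errors. It adds: "The same KM methods will be applied for the final efficacy analysis". No covariate or stratum enters.

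**Randomisation.** Section 6.3 specifies "block randomization by Canadian region and patient weight". Weight group is among the 12 variables in section 8.3. Region is not, and it is also missing from the baseline tables (section 9.4 and mock Table 1) and from every efficacy analysis in section 10.

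**Change record.** Section 15 lists the move to Kaplan-Meier and the modified per-protocol set as the notable changes to the final efficacy analysis. It does not revisit the adjustment rule.

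**The concern.** The adjustment rule suits a simple yes/no endpoint. The primary estimator has since changed, and the rule was left as it stood. If the trigger fires, the analyst must decide, with the trial data in hand, what to do with censored children, how to turn an odds ratio into a relative risk, and how the result stands beside the unadjusted one. A plan should settle these three choices in advance.

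The rule also selects the wrong covariates. A baseline p-value in a randomised trial measures chance imbalance, not prognostic importance. The two factors built into the randomisation are the natural candidates for adjustment, yet they are the least likely to enter: region is not on the list, and weight is balanced by design.

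At stake are the credibility and meaning of the adjusted estimate, and some precision. The validity of the primary test is not at stake.

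**Working it through.** **1. The plan's sample size (section 7).** Inputs: 75% v 50%, power 90%, two-sided 0.05, log relative-risk scale. Null variance term: 2 × (1 − 0.625)/0.625 = 1.2. Alternative variance term: 0.25/0.75 + 0.5/0.5 = 1.333. With ln 1.5 = 0.4055:

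n = (1.960 × √1.2 + 1.2816 × √1.333)² / 0.4055² = 80.0 per group.

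A pooled two-proportion formula gives 77. The stated 79 lies between them, and 158/0.9 = 175.6 gives the stated 176. The design figures reproduce, and nothing below changes the sample size.

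**2. Scale.** At the design rates RR = 0.75/0.50 = 1.5, while OR = (0.75/0.25)/(0.50/0.50) = 3.0. The visible part of mock Table 4 has one relative-risk column and no place for an adjusted estimate.

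**3. Censored children.** A plain logistic fit uses only children with a determined outcome. At the interim 27 were determined and 17 were not (17/44 = 38.6%). To illustrate the effect, assume constant hazards, and that a fraction c of each arm is censored uniformly over the year, independently of outcome. Among determined children the success proportion is

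p(1 − c) / [p(1 − c) + (1 − p)(1 − c) + c·e], where e = 1 − (1 − p)/(−ln p).

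Here e = 0.131 at p = 0.75 and 0.279 at p = 0.50.

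| c (assumed) | Intervention | Control | Complete-case RR (true 1.50) |
|---|---|---|---|
| 10% | 0.739 | 0.485 | 1.52 |
| 20% | 0.726 | 0.467 | 1.55 |
| 40% | 0.690 | 0.422 | 1.64 |

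The odds ratio itself hardly moves (3.01 to 3.05). The drift appears once the fit is turned back into a relative risk, which is the scale that the plan needs.

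**4. Other endpoints.** Intolerance, inactive disease and biologic start are analysed by Kaplan-Meier and log-rank, but mock Table 4 also shows n (%), so a logistic model could be fitted to them. It does not suit the two mean scores, which are compared by t-test.

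**5. The trigger.** If the 12 tests are independent, the chance that at least one is flagged is 1 − 0.9¹² = 71.8%; without weight it is 1 − 0.9¹¹ = 68.6%. With 12 equally correlated normal variables it is 64% at correlation 0.3 and 53% at 0.5. A simulation with seven correlated continuous variables (correlation 0 to 0.6), sex at 70%, uveitis at 12%, two multi-category tests at 9% each and weight never flagged gives 52-65%, with about one variable flagged on average. The correlations and prevalences are assumptions; the SAP gives none.

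**6. Cost of leaving out region and weight.** Suppose that stratum success rates vary with standard deviation s around the arm mean. Blocking then reduces the true arm variance to [p(1 − p) − s²]/n, while the unadjusted interval still uses p(1 − p)/n.

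| s (assumed) | CI-width ratio, both arms 50% | CI-width ratio, 75% v 50% |
|---|---|---|
| 0.05 | √(0.25/0.2475) = 1.005 | 1.005 |
| 0.10 | √(0.25/0.24) = 1.021 | √(1.3333/1.2756) = 1.022 |
| 0.15 | √(0.25/0.2275) = 1.048 | √(1.3333/1.2033) = 1.053 |

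The unadjusted interval is therefore slightly too wide, which is conservative. The SAP gives no region or weight effect from which to choose s.

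**The case against.** **Logistic regression can yield an adjusted relative risk.** With standardisation, and with censoring weights or pseudo-values, it can. This stands, so the defect is that the analysis cannot be done as specified, not that it is impossible.

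**The interim share of undetermined outcomes overstates the problem.** This also stands. Those 17 children were still on trial. The final analysis waits 60 weeks after the last recruit (section 10), and later registry visits count towards success (section 10.1). The final share is unknown and probably smaller, although section 9.3 does not expect it to be zero.

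**The scale difference does not affect the test.** The final null is rejected if the interval lies above 1, and RR = 1 coincides with OR = 1. That is fair. A reader might also fear that an adjusted odds ratio would be mistaken for a relative risk, but nothing in the SAP shows that this would happen. The point is one of estimation and labelling.

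**The p<0.1 rule is pre-specified and uses only baseline data.** True, so it is not a free choice of covariates. It remains a poor selection rule, and it makes it more likely than not that the undefined analysis will be called for.

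**A new rule would be a change made after an open-label interim.** This is a reason to record the change openly and keep it supportive. It is not a reason to leave the rule undefined.

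**A stronger reading.** A reader might infer that the primary result is biased, or that its false-positive rate is inflated by ignoring region and weight. The documents do not support this. Sections 10.1 and 15 most naturally make the unadjusted Kaplan-Meier relative risk decisive, and ignoring factors balanced by design tends to widen the interval.

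**Conclusion.** The point holds as an inconsistency between the adjustment rule and the primary estimator. Followed as written, the rule calls for an adjusted analysis in roughly 52-72% of trials by chance alone. It then supplies a model with no rule for censored children, on the odds-ratio scale, with no stated status beside the primary result. Region cannot enter that model, and weight will rarely do so.

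The precision cost is modest and its size is unknown from the SAP: about 2-5% in interval width if stratum success rates vary with an assumed SD of 10-15 percentage points, and negligible at 5 points. These figures are illustrative only. The matter should be corrected before the final analysis, but it does not threaten the confirmatory test.

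**What to change.** 1. State in sections 8.3 and 10 that the unadjusted Kaplan-Meier relative risk at week 52 is the confirmatory result, as at the interim.
2. Remove the p<0.1 trigger and the logistic models. Replace them with one pre-specified supportive week-52 relative risk, adjusted for region and weight group whatever the baseline p-values. Use a method that keeps censoring and the relative-risk scale, for example stratum-weighted Kaplan-Meier or log-link pseudo-value regression.
3. Set a rule in advance for merging sparse strata.
4. Report the adjusted result in Table 4, labelled supportive, and add region to Table 1.
5. Record this in section 15 as a change made after the interim analysis.

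**Cost:** SAP wording and modest programming. The confirmatory test, the sample size and the completed interim are unaffected. The downsides are possible sparse strata (the number of regions is not stated, and the lightest weight group may be small) and a precision gain that may be slight.
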